We also removed the RETAIN verbal consent question about "research attitudes questions" and eliminated the practice of placing patients on the RETAIN or non-RETAIN pathway depending on their response to the eligibility probe. This approach is consistent to the Phase III MOVE-IT study protocol and ensured uniform approaches across the two minimal risk studies, while also optimizing practicability of the research for the BASC team.

c. Phases II and III - Modification to the BASC and MOVE-IT debriefing scripts

We removed the question, "When you agreed to participate in the [MOVE IT or smoking cessation study], did you know that all participants would receive up to [maximum RETAIN incentive amount] in the end?" from Phase II (BASC) and Phase III (MOVE IT) debriefing scripts. After speaking with the RETAIN study's biostatistician, we determined that these data would not be useful for analyses, nor effective at ascertaining post-hoc contamination in these companion studies.

3. Approved September 26, 2017

a. Phases II and III - Modifications to the Compared Riskiness Scale

It was determined by the trial's faculty statistician and data manager that the items in the 9-item Compared Riskiness Scale should contain activities that are more aligned in risk-level and the probability, as well as nature, of consequences of participation in trials like the BASC and MOVE IT, as opposed to the lung cancer trial RTOG 1308. Several items were replaced to better align these risky activities and enable a range of responses from participants, including "taking 3 times the recommended dose of pain killers;" "receiving stitches;" "riding a motorcycle with no helmet;" "getting a body piercing;" and "bungee jumping."

4. Approved October 25, 2017

a. Phases II and III - Clarification of Payment Procedures

Debriefing scripts, recruitment procedures, and FAQs for both BASC and MOVE-IT trials were modified to clarify the procedures and timing for subject compensation.

Compensation information available to BASC subjects (if requested) during recruitment:

"When do I get compensated (if randomized to the \$200/\$500)?"

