As a result of both the successes of the Phase II and Phase III collaborations, and the shortcomings of the Phase I 1308 collaboration, the RETAIN team decided to end our collaboration with 1308 and focus all resources squarely on the Phase II and Phase III collaborations. This decision was discussed with the 1308 investigators on November 27 and the RETAIN team received approval to move forward exclusively focused on Phases II and II from the sponsor, the Nation Cancer Institute, on November 30, 2017.

As a result of this change, the team removed RTOG 1308-relevant language from the IRB protocol and ended Penn's oversight of the RETAIN trial at MDACC, a relying institution. The MGH and Washington University research teams closed out the RETAIN study at their respective sites.

7. Approved January 25, 2018

a. Phase II – Modification to BASC screening procedures

The study teams for BASC and RETAIN implemented a RETAIN-related change to the phone screen script being used at Northwestern and Penn. For patients randomized to RETAIN, the team stopped asking, "Does this sound like something that you are interested in?" before administering the RETAIN surveys. They simply transitioned from introducing the study basics to administering the RETAIN questions by saying, "Now we ask that you answer a few more questions before finalizing the details of your intake visit."

The goal of this change was to provide an opportunity to capture RETAIN baseline data that was not being collected systematically due to early withdraws from the phone screen call.

b. Phases II and III - Revisions to the Compared Riskiness Scale

The study team examined the phrasing for the Compared Riskiness scale in an Amazon mechanical Turk study aimed at countering floor effects in our measure of risk perception. As a result of this investigation we made several changes to the phrasing of the questions in the scale. We did not add new items to the scale.

8. Approved February 21, 2018

a. Phase II – Modification to MOVE IT recruitment procedures

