This modification was submitted in tandem with our colleagues on the Mobility, Outcomes, and Validated Experiences Incentive Trial (MOVE IT) study (IRB # 823491). With this change MOVE IT eligibility was assessed earlier in the enrollment process order to randomize and announce the incentives earlier to patients. We also added a note to patients randomized to the \$100 and \$300 arms that they can receive the first installment of their payment the day they decide to participate. We modified the modality of payments such that the first payment would be administered via ClinCard to ensure that all patients who enroll can go get the first installment in a non-check format. These changes were reflected in the updated debriefing and consent forms.

b. Phases II and III – Modifications to the Compared Riskiness Scale

We also updated the Compared Riskiness scale once more in an effort to counter early floor effects.

9. Approved April 23, 2018

a. Phase III – Modification to data collection and administration of surveys

In our modification approved February 21, 2018, we moved the randomization to 1 of 3 incentives to earlier in the clinical research coordinators' recruitment script to optimize the research team's ability to augment enrollment in the MOVE IT study. Patients who are randomized in this model become RETAIN subjects, and we had a way to capture demographic information on RETAIN subjects who decline participation in MOVE IT. However, we did not have a means of capturing risk perception data on patients who declined early, before reading the consent form for MOVE IT. To mitigate the issue of data missingness among these patients and to ensure we were able to execute the study successfully, we decided to include the Compared Riskiness survey in the baseline set of surveys, as well as include a minimal description of risks and benefits early in the enrollment script. This modification and change in data collection allowed us to test the interaction between incentive size and risk perception on the outcome of enrollment – and detect undue inducement, a key outcome of the study and criterion for the Data Safety and Monitoring Board to consider stopping the trial.

10. Approved January 25, 2019

a. Phase III – Addition of Qualitative Evaluation of Patient Decision-Making

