the outcome of enrollment in the parent trials. We will test two interactions, each in a separate model to avoid collinearity, to determine if incentives represent unjust inducements: that between incentive size and the primary covariate of annual household income, and that between incentive size and the primary covariate of economic well-being. All analyses will be stratified by parent study.

Analyses of interaction terms will be structured as tests of non-inferiority. The null hypothesis, for both trials, will be that the use of incentives meets criteria for undue or unjust inducement. We can reject the null, and conclude the absence of undue or unjust inducement, if the interaction terms are "small" according to pre-specified criteria (in technical terms, the inferiority margin). Said a different way, our analyses are designed to determine if we can exclude the possibility that incentives represent undue or unjust inducements if the resulting interaction terms are sufficiently small. Specifically, we will use one-sided alpha levels of 0.05 to exclude, with 95% confidence, the possibility that any of these interaction odds ratios are >2.0.

We will explore temporal trends in incentives' effects over the study period using stratified analyses. If temporal trends are noted, as may occur if prospective patients learn of the incentives used in these studies, we will adjust for their influence by entering time as a covariate, modeled as a spline. We will evaluate potential effect modifiers (variables in Table 1) using stratified analyses. If differences among strata appear, we will formally test their corresponding interactions with the incentive amount.

TABLE 1 FACTORS FOR ADJUSTMENT AND EXPLORATION OF EFFECT MODIFICATION

Potential factors for adjustment			
Patient level covariates	Variable coding or definition		
• Age	Continuous		
• Gender	Binary		
• Race	Categorical		
Marital status	Categorical		
Education	Categorical		
Income	Categorical		
Economic well-being	Categorical		
Prior research participation	Categorical		
Attitudes towards research:	Continuous, measured using the Research Attitudes Questionnaire-7 (RAQ- 7).		

6. Secondary analysis

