We will implement secondary interaction analyses of risk score with incentive arm. Risk score will be treated as binary variable with 0 and >0 categories and Incentive will be treated as ordinal factor. The analysis method will be same as described in section **c**. We plan to compare the inference of this analysis with the primary approach and report accordingly.

a. Approach to outliers and influential observations

We plan to perform diagnostic checks for influential and outlier observations in interaction analyses. The analyses will be done both ways including and then excluding influential observations if any is detected. To implement the diagnostic process we will use 'car' package from R.

b. Secondary outcome measures

Attention to the informed consent document: We will assess the amount of time patients spend reading each part of the parent trial consent form by setting up each section as a "survey" in REDCap. The data extract will include the time – to the second – at which the participant moved to another section through a timestamp. The primary measure of this assessment will be time spent on the risk section; the secondary measure will be total time spent on the consent form.

Perceived risks of the research: Perceived risks of the research will be measured by a modified 9-item "compared riskiness" scale, which has been used in previous studies and refined for the RETAIN trial.

Incidence of therapeutic misconceptions: It has been hypothesized that the use of financial incentives could reduce therapeutic misconceptions, and thereby promote informed decision-making. Because patients are not accustomed to being paid for their clinical care, offering incentives could signal that research is different. We will test the hypothesized benefit of research incentives by measuring the incidence of therapeutic misconception in each incentive arm. We will assess this outcome with a 4-item therapeutic misconception tool, developed by External Advisory Board member, [name].

Understanding of the trial: To assess whether increased attention translates into improved understanding of the trial, we will use a 6-item Trial Elements Quiz, featuring core elements of the parent trials' consent forms.

Perceptions of influence or coercion: To measure general perception of coercion and voluntariness of research participation, we will use the five-item Perceived Coercion Scale of the MacArthur Admission Experience Survey.

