The target enrollment of 576 patients in each RETAIN sub-trial was determined based on the primary goal of ruling out the possibility that incentives represent an undue inducement. Statistically, the presence of an undue inducement is represented by the interaction term between incentive amount and risk on the outcome of enrollment in the parent trial. Thus, we seek to rule out the possibility that the odds ratio associated with this interaction term is appreciably greater than a null value. To facilitate such a power estimation, we considered groups of participants with greater or less than the median level of risk perception who will be randomized to the highest incentive versus the lowest incentive. With an overall sample size of 576 participants in each parent study involved in the RETAIN trial, we assumed that 192 participants would be randomized to each of the 3 incentive arms. Assuming that randomization balances the incentives distribution within each risk-perception group, 96 participants will be assigned to each of the 3 incentives within both the high and low risk-perception groups. Among patients assigned to receive \$0, we set the OR contrasting the odds of enrollment between riskperception groups to 1, such that the OR for those assigned to receive the highest incentive (\$300 or \$500, in MOVE IT and BASC, respectively) represents the interaction odds ratio. We assume a true interaction OR of 1, and use a one-sided significance level of 0.0427 such that the upper 95.73% confidence limit on the observed OR falls entirely below the non-inferiority threshold. If the enrollment rate in the parent trials is 50%, we will have at least 80% power to rule out undue inducement, as represented by an interaction odds ratios of 2.0 or greater. However, because we will actually analyze risk as a continuous variable and incentive size as a 3-level variable, our true power will be greater than the estimates reported here. Similar analyses suggest similar levels of power to rule out the unjust inducement interaction terms.

8. Data Safety & Monitoring Board (DSMB)

We have chartered a DSMB to monitor RETAIN, with purview over both embedded trials, for the expressed purpose of evaluating evidence of undue or unjust inducement. Any serious adverse events, protocol deviations/violations, and unanticipated events will be reported to the IRBs with oversight of recruiting sites, the DSMB, and The National Cancer Institute.

9. Stopping Rules

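### The Compared Riskiness Scale was changed four times, yet the primary risk-by-incentive model pools all scores with no handling of scale version, which can bias the non-inferiority test in a direction and by an amount that the documents leave open

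*Combined protocol and SAP*

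**What the plan says.** Changes to Protocol lists these revisions of the scale:

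- **September 2017 (item 3.a, both trials):** "Several items were replaced to better align these risky activities and enable a range of responses from participants".
- **November 2017 (item 5.c, BASC only):** the lead-in to the items was reworded to draw a Yes/No answer.
- **January 2018 (item 7.b, both trials):** "we made several changes to the phrasing of the questions in the scale". No items were added.
- **February 2018 (item 8.b, both trials):** "We also updated the Compared Riskiness scale once more in an effort to counter early floor effects". The content of this update is not described.

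Item 9.a (April 2018) also moved the scale into the baseline surveys in MOVE IT, ahead of the consent form.

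Final SAP 6.b describes a single instrument: "Perceived risks of the research will be measured by a modified 9-item" comparison scale. Section 5.c puts that score into one risk-by-incentive model per parent trial, with enrolment as the outcome. Section 7.b says that risk is analysed as continuous. Neither the text of 5.c nor its Table 1 mentions scale version. The nearest provisions are stratified looks at temporal trends in the incentive effect, a spline for time if trends appear (5.c), a secondary analysis of the score as 0 versus above 0 (6), and influence diagnostics (6.a).

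**The concern.** Scores from different wordings or item sets need not share a mean, a spread or an error variance. If they are pooled as one variable, part of the variation in that variable is variation between versions, which says nothing about a patient's perceived risk.

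In a superiority test this would mostly cost power. Here the claim is that an interaction odds ratio of 2.0 can be excluded, so attenuation toward 1 makes the claim easier to reach. Randomisation in blocks of 3 and 6 keeps versions roughly balanced across arms. Version is therefore not confounded with arm, but balance does not prevent attenuation. The affected model answers the primary aim and is the one that set the sample size.

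**Working it through.** **The plan's own figure.** Final SAP 7.b states at least 80% power. Its inputs are "With an overall sample size of 576 participants in each parent study", then "96 participants will be assigned to each of the 3 incentives within both the high and low risk-perception groups", 50% enrolment, a true odds ratio of 1, a margin of 2.0, and the instruction to "use a one-sided significance level of 0.0427".

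- With the $0-arm odds ratio fixed at 1, SE = √(2/(96 × 0.25)) = 0.289. Power = Φ(0.693/0.289 − 1.720) = 75.2%.
- For the full four-cell contrast, SE = √(4/24) = 0.408 and power is 49.1%.
- With risk continuous and the odds ratio taken per SD, power is about 95%.

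The stated figure is therefore not reproduced, and power depends on a risk unit that the SAP does not give. Section 5.c also uses a different level: "we will use one-sided alpha levels of 0.05 to exclude, with 95% confidence". These are separate points, but the missing unit matters below.

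**Did anyone answer an earlier version?** Original SAP section 1 says that it was finalised after RTOG 1308 was dropped and before any BASC or MOVE IT enrolment. Changes to Protocol item 6 dates that decision to November 2017. Item 7.a (January 2018) changes the BASC call for patients already randomised to RETAIN, because baseline data were being lost. Final Protocol 8.d places the risk scale in that call. Item 8.b refers to floor effects already seen. This indicates BASC patients on versions before January or February 2018. For MOVE IT the evidence is weaker. No counts are given.

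**Size of the effect.** Let R be the final-version score (SD 1), X the pooled score, and f the share on an earlier version. To a close approximation

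ln OR(pooled) ≈ λ × ln OR(true), with λ = Cov(X,R)/Var(X).

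Multiplying by SD(X) gives the odds ratio per SD of the pooled score. For a true odds ratio of 2.0 (lowest to highest arm, per SD) and an assumed f = 20%:

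| Earlier version | Cov | Var | λ | OR, raw score | OR, per pooled SD |
|---|---|---|---|---|---|
| mean lower by 0.5 SD | 1 | 1 + 0.16 × 0.25 = 1.04 | 0.962 | 1.95 | 1.97 |
| mean lower by 1 SD | 1 | 1 + 0.16 × 1 = 1.16 | 0.862 | 1.82 | 1.90 |
| mean lower by 2 SD | 1 | 1 + 0.16 × 4 = 1.64 | 0.610 | 1.53 | 1.72 |
| all at one value, 2 SD below the mean | 0.8 | 0.8 + 0.16 × 4 = 1.44 | 0.556 | 1.47 | 1.59 |
| added noise of 1 SD | 1 | 1 + 0.2 = 1.2 | 0.833 | 1.78 | 1.88 |
| spread halved only | 0.9 | 0.8 + 0.2 × 0.25 = 0.85 | 1.059 | 2.08 | 1.97 |

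Logistic simulation at 20% gives 1.92 to 1.95 for 0.5 SD, 1.81 to 1.90 for 1 SD, and 1.4 to 1.7 for 2 SD or near-total flooring. At 25%, formula and simulation agree: 1.79 and 1.79 for a 1 SD shift, 1.74 and 1.73 for noise, 2.11 and 2.11 for halved spread.

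A simulated 9-item Yes/No count, with harder items in the earlier version and a true value of 2.0 per SD of the final score, gave per-SD values of 1.86 to 1.95 (10% affected), 1.71 to 1.88 (25%) and 1.53 to 1.79 (50%).

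**False non-inferiority at a true odds ratio of 2.0** (N = 576, one-sided 0.05, 4,000 simulated trials per setting). With no mixture the rate is 5.5%.

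| Share affected | Earlier version | Rate |
|---|---|---|
| 10% | 0.5 SD lower | 5.4% |
| 25% | 0.5 SD lower | 7.1% |
| 25% | 1 SD lower | 15.9% |
| 50% | 1 SD lower | 18.3% |
| 25% | spread halved | 2.7% |
| 50% | spread halved | 1.7% |

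**Do the existing provisions help?** A version main effect, which is the most that a time spline could imitate, moves the pooled value only from 1.79 to 1.80 (25%, 1 SD). The 0 versus above 0 coding also mixes versions, because a floored version puts more patients at 0. In a simulated 9-item count its interaction fell from 2.38 with no mixture to 2.24 at 25% and 2.18 at 50%. Full version interactions bring the estimate back to about 2.0.

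**The case against.** **Exposure may be small or nil.** On the Original SAP's statement, the item replacement and the BASC lead-in change reached no analysed patient, and these are the two changes most likely to alter the scale. The lost phone-call data concern BASC only. This stands as a reason to ask for counts. It does not remove the conflict, because the January 2018 entry speaks of randomised patients.

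**A reader might infer that pooling does pull the interaction toward 1, so that the test is anti-conservative.** The documents do not support this as fact. Compression alone raises the per-point odds ratio (2.06, 2.11 and 2.34 at 10%, 25% and 50%) and makes the test conservative. At a true odds ratio of 1, pure mismeasurement causes no bias. Script changes in the same months could act either way: if the incentive effect on enrolment also changed between versions, the pooled value at a true 1 ranged from 0.89 to 1.12.

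**A reader might also infer that an interaction above the margin would slip below it with only 10% to 20% affected.** That needs extreme assumptions. For a true 2.5, the pooled value is 1.96 at 10% if the earlier version sat wholly at the floor, and 1.94 at 20% for a 2 SD shift. For a 0.5 SD shift at 20% it is 2.41 on the raw score and 2.45 re-standardised. The final version was itself sparse, since Changes to SAP reports over 85% of scores at 0 in the ambulation trial. With assumed shares at 0 of 85% (final) and 95% (earlier) and 20% affected, the per-SD value went only from 2.51 to 2.39, and the per-point value rose from 5.47 to about 5.6.

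The SAP's trend checks, binary coding and diagnostics are sensible, but none of them is an adjustment for version.

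**Conclusion.** The gap is real: four recorded changes to the instrument, and a primary model that treats its scores as one measure. Pooling can bias the interaction. The direction depends on how the versions differ, and the size depends on how many patients answered each one. A floor is the problem that the log describes, and a floored earlier version tends to move the per-SD odds ratio toward 1, in favour of the non-inferiority claim. With 20% affected, a modest shift costs a few hundredths on an odds ratio of 2.0, a 1 SD shift costs 0.1 to 0.2, and larger losses need near-total flooring or a 2 SD shift. The shares, shifts and noise levels are all assumptions. If the count on superseded versions is zero, the bias is zero and a table settles the matter. The documents support asking for a cheap check, not a finding that the non-inferiority result is biased.

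**What to change.** 1. Tabulate patients by scale version, parent trial and arm. In MOVE IT, also record whether the scale came before or after the April 2018 move.
2. In SAP 5.c, add version, version-by-risk and version-by-arm terms to the risk model. These handle differences in level and changes in the incentive effect. If versions differ in noise or spread, a common interaction is still an average over versions, so the three-way term or the next analysis is needed.
3. Pre-specify the final-version-only interaction as a sensitivity analysis, reported beside the pooled one. Qualify the non-inferiority conclusion if the two disagree about the 2.0 margin. There is no need to make both a condition of the claim.
4. State the unit of risk score to which the margin applies. Standardising within version is not a safe substitute: it divides by a very small SD in a floored version and changes that unit.
5. Reconcile Original SAP section 1 with Changes to Protocol items 7 and 8 on when BASC and MOVE IT enrolment began.

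**Cost.** The work uses data already held and takes a few degrees of freedom. The final-version-only interval is wider on the log scale: 1/√0.8 = 1.12, about 12%, if 20% are excluded, and 1/√0.6 = 1.29, about 29%, if 40% are.

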[name] (Co-I) is an Assistant Professor of Medicine and Health Care Management at the Perelman School of Medicine and The Wharton School at the University of Pennsylvania is the Co-Investigator for the Mobility, Outcomes, and Validated Experiences Incentive Trial, or MOVE IT.

c. Participating Parent Trial Sites

Parent Trial	Site Name	Location
BASC	Northwestern University	Chicago, IL 60611
	The University of Pennsylvania	Philadelphia, PA 19104
MOVE IT	The Hospital of the University of Pennsylvania	Philadelphia, PA 19104

The RETAIN trial will be conducted at two sites participating in the BASC parent trial, Northwestern University and the University of Pennsylvania; and one site participation in the MOVE IT parent trial, the Hospital of the University of Pennsylvania. These institutions are imbued with substantial research infrastructures and offer close proximity of site PIs to the clinics from which patients will be recruited. Each parent trial supports research staff; in collaboration with the Site PIs, the parent trial research staff will carry out the protocol at their respective institutions.

5. Study Design

This study is a prospective randomized controlled trial nested within two randomized controlled trials.

a. BASC Schema

b. MOVE IT Schema

c. Key Study Design Elements across Parent Trials

	BASC	MOVE IT
Is there a separate step to screen for RETAIN- specific eligibility? Please see Section 8.b. Eligibility.	Yes Patients will be probed for prior knowledge of incentive randomization, equalization, or the maximum amount offered under RETAIN.	Νο
Do patients actively consent to the RETAIN trial? Please see Section 8.d.	No A waiver of consent for RETAIN has been approved by the IRB.	No A waiver of consent for RETAIN has been approved by the IRB.
Can anyone enroll in the parent trial without enrolling in RETAIN?	Yes, if they screen ineligible specifically for RETAIN	Νο
Incentive for parent trial subjects not enrolled in RETAIN Please see Section 6.d. Subject Remuneration.	\$200	Not applicable
Incentive levels Please see Section 7. Randomization.	Low: \$0 Middle: \$200 High: \$500	Low: \$0 Middle: \$100 High: \$300
Debriefing Plan Please see Section 8.h.	On the phone , before the first day of the assigned intervention for the parent trial.	In-person , during the same encounter as all RETAIN procedures and prior to beginning the assigned intervention for the parent trial.
Payments to subjects consented to RETAIN and the parent trial Please see Section 6.d	\$300 in two \$150 installments, plus up to	\$300 in two \$150 installments

Key elements in study design across thetwo parent trials are highlighted in the table and figure below.

\$200 from individual	
session/travel payments. ²	

d. Duration

Patient recruitment began in August 2016. The trial is slated to conclude June 30, 2020, following the development of a manuscript and dissemination of our findings.

i. BASC

RETAIN procedures will be conducted over two phone calls and one in-person visit across one day to three weeks, depending on the intake scheduling capacity of the Penn and Northwestern clinics. RETAIN procedures will commence during the initial pre-screening eligibility assessment for BASC participants, which takes place before participants' first in-person or "intake" visit with BASC research staff. This phone assessment, which reduces the likelihood that BASC participants will attend an intake session only to learn that they are ineligible, is a pre-screening encounter during which participants first learn basic details of the BASC trial. If eligible for RETAIN, they will be randomized and complete the first set of RETAIN assessments over the phone. RETAIN assessments will take 10 additional minutes during the initial phone eligibility call (see Section 8.f. Administration of Survey Instruments).

Participants who pass the BASC pre-screening on the phone will schedule a baseline intake visit. During the baseline intake visit, RETAIN assessments, including the BASC consent process, will constitute 20-30 additional minutes of the encounter. Next, for all consenting BASC participants who have been randomized and enrolled to RETAIN, research staff will place a reminder call immediately prior to their first visit once enrolled on the study; during this call, all RETAIN-randomized, BASC-consented patients will be debriefed and learn of the payment procedures. The debriefing process will take 10-15 minutes during the reminder call. In total, we do not expect the length of a subject's participation time in the study will exceed two hours.

ii. MOVE IT

